10.83 Reporting of Pregnancy and Lactation to Merck

Although pregnancy and infant exposure during breast feeding are not considered adverse events, it is the responsibility of investigators or their designees to report any pregnancy or lactation in a participant (spontaneously reported to them) that occurs during the study.

Pregnancies and infant exposures during breastfeeding that occur after the consent form is signed but before treatment allocation/randomization must be reported by the investigator if they cause the participant to be excluded from the trial, or are the result of a protocol-specified intervention, including but not limited to washout or discontinuation of usual therapy, diet, placebo treatment or a procedure.

Pregnancies and infant exposures during breastfeeding that occur from the time of treatment allocation/randomization through 120 days following cessation of Sponsor’s product, or 30 days following cessation of treatment if the participant initiates new anticancer therapy, whichever is earlier, must be reported by the investigator. All reported pregnancies must be followed to the completion/termination of the pregnancy. Pregnancy outcomes of spontaneous abortion, missed abortion, benign hydatidiform mole, blighted ovum, fetal death, intrauterine death, miscarriage and stillbirth must be reported as serious events (Important Medical Events). If the pregnancy continues to term, the outcome (health of infant) must also be reported.

Such events must be reported within 24 hours to the Sponsor and within 2 working days to Merck Global Safety. [REDACTED]

10.84 Immediate Reporting of Adverse Events to the Sponsor and to Merck

A serious adverse event is any adverse event occurring at any dose or during any use of Merck’s product that:

- Results in death;
- Is life threatening;
- Results in persistent or significant disability/incapacity;
- Results in or prolongs an existing inpatient hospitalization;
- Is a congenital anomaly/birth defect;
- Is an other important medical event
- **Note:** In addition to the above criteria, adverse events meeting either of the below criteria, although not serious per ICH definition, are reportable to the Merck in the same timeframe as SAEs to meet certain local requirements. Therefore, these events are considered serious by Merck for collection purposes.
 - Is a new cancer (that is not a condition of the study);
 - Is associated with an overdose.

For the time period beginning when the consent form is signed until treatment allocation/randomization, any serious adverse event, or follow up to a serious adverse event, including death due to any cause that occurs to any participant must be reported within 24 hours to the Sponsor and within 2 working days to Merck Global Safety if it causes the participant to be excluded from the trial, or is the result of a protocol-specified intervention, including but not limited to washout or discontinuation of usual therapy, diet, placebo treatment or a procedure.

For the time period beginning at treatment allocation/randomization through 90 days following cessation of treatment, or 30 days following cessation of treatment if the participant initiates new anticancer therapy, whichever is earlier, any serious adverse event, or follow up to a serious adverse event, including death due to any cause whether or not related to the Merck product, must be reported within 24 hours to the Sponsor and within 2 working days to Merck Global Safety.

Additionally, any serious adverse event, considered by an investigator who is a qualified physician to be related to Merck product that is brought to the attention of the investigator at any time following consent through the end of the specified safety follow-up period specified in the paragraph above, or at any time outside of the time period specified in the previous paragraph also must be reported immediately to Merck Global Safety.

All participants with serious adverse events must be followed up for outcome.

SAE reports and any other relevant safety information are to be forwarded to the Merck Global Safety facsimile number: [REDACTED]

A copy of all 15 Day Reports and Annual Progress Reports is submitted as required by FDA, European Union (EU), Pharmaceutical and Medical Devices agency (PMDA) or other local regulators. Investigators will cross reference this submission according to local regulations to the Merck Investigational Compound Number (IND, CSA, etc.) at the time of submission. Additionally investigators will submit a copy of these reports to Merck & Co., Inc. [REDACTED]

[REDACTED] at the time of submission to FDA.

10.85 Events of Clinical Interest

Selected non-serious and serious adverse events are also known as Events of Clinical Interest (ECI) and must be reported within 2 working days to Merck Global Safety. [REDACTED]

For the time period beginning when the consent form is signed until treatment allocation/randomization, any ECI, or follow up to an ECI, that occurs to any participant must be reported within 2 working days to Merck Global Safety if it causes the participant to be excluded from the trial, or is the result of a protocol-specified intervention, including but not limited to washout or discontinuation of usual therapy, diet, placebo treatment or a procedure.

For the time period beginning at treatment allocation/randomization through 90 days following cessation of treatment, or 30 days following cessation of treatment if the participant initiates new anticancer therapy, whichever is earlier, any ECI, or follow up to an ECI, whether or not related to Merck product, must be reported within 2 working days to Merck Global Safety.

Events of clinical interest for this trial include:

1. An overdose of Merck product, as defined in Section 10.82, that is not associated with clinical symptoms or abnormal laboratory results.
2. An elevated AST or ALT lab value that is greater than or equal to 3X the upper limit of normal and an elevated total bilirubin lab value that is greater than or equal to 2X the upper limit of normal and, at the same time, an alkaline phosphatase lab value that is less than 2X the upper limit of normal, as determined by way of protocol-specified laboratory testing or unscheduled laboratory testing.*

*Note: These criteria are based upon available regulatory guidance documents. The purpose of the criteria is to specify a threshold of abnormal hepatic tests that may require an additional evaluation for an underlying etiology.

11.0 Treatment Evaluation/Measurement of Effect

Patients must have measurable disease.

The primary endpoint is the evaluation of cutaneous disease as measured by mSWAT (5). Disease progression will also be measured by lymph nodes, visceral disease and blood.

11.1 Definitions of Measurable

11.11 Measurable Disease

- 11.111 A primary cutaneous lesion is measurable if detectable through standard full body skin examination. Documentation by color photography is required.
- 11.112 A visceral lesion is considered measurable if its longest diameter can be accurately measured as 2.0 cm with chest x-ray, or as ≥ 1.0 cm with CT scan, CT component of a PET/CT, or MRI.
- 11.113 A malignant lymph node is considered measurable if its short axis is ≥ 1.5 cm when assessed by CT scan (CT scan slice thickness recommended to be no greater than 5 mm).

11.2 Evaluation of Measurable Disease

11.21 Evaluation of primary cutaneous lesion

mSWAT is calculated using body surface area (BSA) of each MF lesion (palm plus fingers of the patient $\approx 1\%$ BSA) in each of 12 areas of the body, multiplying the sum of the BSA of each lesion type by a weighting factor (patch=1, plaque=2, and tumor =4) and generating a sum of the subtotals of each lesion subtype.

11.211 Measurement of effect

- Overall cutaneous response rate (ORR) = proportion of patients with a 50% or greater reduction of baseline mSWAT score
- Complete cutaneous response rate (CR) = proportion of patients with a 100% reduction of baseline mSWAT score
- Cutaneous 90 response rate (CR90) = proportion of patients with a 90% or greater reduction of baseline mSWAT score without the development of new tumors
- Cutaneous partial response rate (PR) = proportion of patients with a 50-90% baseline reduction of mSWAT score without the development of new tumors
- Progressive cutaneous disease (PD) = greater than 25% increase in baseline mSWAT or the development of new tumors. However, if in the judgement of the investigator, the increase in mSWAT is the result of inflammation due to treatment and/or the unmasking of subclinical skin involvement, this increase in mSWAT shall not be considered evidence of progressive cutaneous disease and the patient shall otherwise be classified as stable cutaneous disease (SD).
- Stable cutaneous disease (SD) = <25% increase to <50% reduction in baseline mSWAT without the development of new tumors ; or patients with a greater than 25% increase baseline mSWAT due to

the result of inflammation due to treatment and/or the unmasking of subclinical skin involvement.

- Relapsed cutaneous disease = Any disease recurrence in those with complete response

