11.5 Overall Objective Status

Overall systemic response rate is defined as 50% or greater reduction of baseline mSWAT score without evidence of progressive nodal, visceral, or blood involvement.

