16.0 Statistical Considerations and Methodology

16.1 Overview

This is a phase II study designed to assess the overall cutaneous response rate at cycle 9 in MF patients treated with pembrolizumab. It is a single one-stage design with an interim analysis based on the Simon optimal design with 85% power and 10% Type I error.

NOTE: As per Amendment 4, accrual will cease after the enrollment of 10 patients due to sponsor decision on funding. Thus, the study power and type I error will not be appropriate for the analysis, as the study will not be able to go to full accrual. The study will be analyzed at the pre-defined interim step.

16.11 Endpoint:

The primary endpoint is overall cutaneous response (cutaneous complete response (CR), cutaneous 90 response (CR90) or cutaneous partial response (PR)) as defined using the mSWAT score as stated in section 11.0. Throughout Section 16.0, CR, CR90 or PR will be considered synonymous with “success”, unless specified otherwise. All patients meeting the eligibility criteria who have signed a consent form and have begun treatment will be evaluable for response.

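### Systemic response in 11.5 does not exclude new skin tumours, so a patient with cutaneous progression can be counted as a systemic responder

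*Combined protocol and SAP*

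**What the plan says.** Section 11.211 lists the cutaneous categories:

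- Overall response: "proportion of patients with a 50% or greater reduction of baseline mSWAT score". Nothing is said about new tumours.
- Complete response: "Complete cutaneous response rate (CR) = proportion of patients with a 100% reduction of baseline mSWAT score".
- CR90: "proportion of patients with a 90% or greater reduction of baseline mSWAT score without the development of new tumors".
- PR: "proportion of patients with a 50-90% baseline reduction of mSWAT score without the development of new tumors".
- PD: "greater than 25% increase in baseline mSWAT or the development of new tumors". Either limb is enough. The exception for inflammation or unmasked disease excuses a rise in mSWAT; it does not mention new tumours.

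Section 11.5 then states: "Overall systemic response rate is defined as 50% or greater reduction of baseline mSWAT score without evidence of progressive nodal, visceral, or blood involvement". The skin is not among the sites where progression disqualifies.

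Section 16.11 defines the primary endpoint as CR, CR90 or PR and gives the word success that meaning throughout Section 16 unless otherwise specified. Section 16.42 reports the systemic response proportion as a secondary outcome and adds no further condition. Section 13.2 labels patients who develop PD as non-responders, in its sentence on cycle 1.

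**The concern.** A response category and a progression category should not both apply to one patient at one assessment. Here they can. A new tumour is enough for cutaneous PD and disqualifies a patient from PR and CR90, but it does not disqualify the patient from systemic response in 11.5 or from the overall response line in 11.211.

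For 11.5, nothing elsewhere in the plan closes the gap, so the secondary systemic response proportion can include patients whose skin disease has progressed. For the 11.211 line, the plan has two non-equivalent definitions of overall cutaneous response, one there and one in 16.11. With accrual stopped at 10 patients under Amendment 4, a single misclassified patient visibly changes a reported rate.

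**Working it through.** **1. The plan's own figures.** Section 16.33 gives a 0.456 probability of passing the interim at a true rate of 0.15. With at least 2 successes needed in 10:

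1 − 0.85^10 − 10 × 0.15 × 0.85^9 = 1 − 0.197 − 0.347 = 0.456.

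This reproduces. The design table does not depend on the point made here.

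**2. How response and PD can coincide.** The first limb of PD (a rise of more than 25% from baseline) cannot occur together with a fall of at least 50% from the same baseline. The second limb (a new tumour) can. Tumour area has weight 4, so a new tumour covering 1% of body surface adds only 4 points.

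Worked case: baseline mSWAT 60, follow-up 25, of which 4 points are one new 1% tumour; no nodal, visceral or blood progression. Reduction = (60 − 25)/60 = 58%.

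| Definition | Section | Met? |
|---|---|---|
| Overall cutaneous response line | 11.211 | Yes |
| CR | 11.211 | No, 58% is below 100% |
| CR90 | 11.211 | No, below 90% and a new tumour |
| PR | 11.211 | No, new tumour |
| Cutaneous PD | 11.211 | Yes, new tumour |
| Overall systemic response | 11.5 | Yes |
| Success | 16.11 | No |

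The pattern does not depend on these values. If all other disease clears and only a new tumour is left:

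- baseline 20, new 1% tumour: (20 − 4)/20 = 80%
- baseline 40, new 2% tumour: (40 − 8)/40 = 80%
- baseline 80, new 2% tumour: (80 − 8)/80 = 90%

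Each is PD and a systemic responder. CR cannot overlap in this way, because any tumour present at the assessment makes the score greater than zero.

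**3. Size for the secondary rate.** With 10 patients, k such patients add k/10 to the systemic response proportion: 10 percentage points for one, 20 for two. The documents give no frequency from which to estimate k.

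**4. Systemic against cutaneous rate.** Let a be the number of patients like the worked case, and b the number of cutaneous responders under 16.11 who have nodal, visceral or blood progression. The systemic count minus the 16.11 cutaneous count is a − b. The systemic rate exceeds the cutaneous rate only when a is larger than b. Against the 11.211 line it can never exceed, because 11.5 is then a subset.

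**5. The 2-of-10 rule, only if the 11.211 line replaced 16.11.** Assumption, not in the documents: a share q of patients with a fall of at least 50% also have a new tumour. If the CR/CR90/PR rate is 0.15, the rate under the 11.211 line is 0.15/(1 − q).

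| q | Rate under the 11.211 line | P(at least 2 of 10) |
|---|---|---|
| 0 | 0.150 | 0.456 |
| 5% | 0.158 | 0.484 |
| 10% | 0.167 | 0.515 |
| 20% | 0.1875 | 0.585 |

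Under 16.11 as written, the first row applies whatever q is.

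**The case against.** The strongest reply is that 16.11 already settles what matters. Success throughout Section 16 is CR, CR90 or PR, and the interim rule in 16.22 counts successes. The patient in the worked case is not one. The 11.211 overall response line has no analysis of its own in 16.42 and can be read as a summary of the categories below it. This stands. A reader might infer that one such patient can turn the 2-of-10 decision, or that the type I error is inflated; the documents do not support either while 16.11 is followed. The 28-patient decision rule is in any case marked not applicable under Amendment 4.

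Some risk of using the wrong line remains. Section 1.23 and 16.1 name the primary measure by the same label as the 11.211 line. Section 16.41 works from mSWAT at baseline and cycle 9 with the last observation carried forward, and that score does not record whether a tumour is new. A patient who leaves at PD has an mSWAT at the end-of-treatment visit, and that is the score that could be carried forward. These are reasons to align the wording, not evidence that the primary analysis is wrong.

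A second reply is that the plan treats PD as non-response in 13.2, and a note ahead of Section 1.0 groups progressive disease with non-response. Both concern patient disposition. Neither is stated as an analysis rule, and neither amends 11.5. They show what was probably intended, which supports correcting 11.5.

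Third, a reader might infer that the systemic rate will exceed the cutaneous rate. That holds only under the condition in step 4.

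**Conclusion.** The point holds for 11.5 under every reading of the plan. As written, a patient with cutaneous PD by new tumour and an mSWAT fall of at least 50% is a systemic responder, at odds with the PD definition in 11.211 and the language of 13.2. The effect is on one descriptive secondary proportion, at 10 percentage points per such patient among 10. It carries no hypothesis test or decision rule.

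For the primary endpoint, the finding is a mismatch between the 11.211 line and 16.11. Because 16.11 governs Section 16, the primary rate and the 2-of-10 rule are affected only if an analyst uses the 11.211 line in its place. The conclusion rests on the definitions alone. Whether any such patient will occur cannot be judged from the documents. It should be corrected before analysis.

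**What to change.** Two edits, using conditions the protocol already has:

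1. In 11.5, add the no-new-tumour condition that CR90 and PR carry, or equivalently exclude cutaneous PD. By step 2 the two forms give the same result for a patient with a fall of at least 50% at that assessment.
2. In 11.211, define overall cutaneous response as CR, CR90 or PR, so that it matches 16.11.

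No new data are needed: the dermatology examination, photography and mSWAT are already scheduled each cycle in 4.1. No threshold, sample size or decision rule changes. The cost is that the reported systemic response rate may be slightly lower. The primary endpoint under 16.11 is unchanged.

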- Post-Baseline Sum of the Dimensions (PBSD): A sum of the longest diameter for all target visceral lesions plus the sum of the short axis of all the target lymph nodes will be calculated and reported as the post-baseline sum of dimensions (PBSD). If the radiologist is able to provide an actual measure for the target visceral lesion (or target lymph node), that should be recorded, even if it is below 0.5 cm. If the target visceral lesion (or target lymph node) is believed to be present and is faintly seen but too small to measure, a default value of 0.5 cm should be assigned. If it is the opinion of the radiologist that the target visceral lesion or target lymph node has likely disappeared, the measurement should be recorded as 0 cm.

- The minimum sum of the dimensions (MSD) is the minimum of the BSD and the PBSD.

11.227 Measurement of effect

- Complete Response (CR): All of the following must be true:
 - a. Disappearance of all visceral lesions.
 - b. Each target lymph node must have reduction in short axis to <1.0 cm.
- Partial Response (PR): At least a 30% decrease in PBSD (sum of the longest diameter for all target visceral lesions plus the sum of the short axis of all the target lymph nodes at current evaluation) taking as reference the BSD (see Section 11.226).
- Progression (PD): At least one of the following must be true:
 - a. At least one new malignant lesion, which also includes any lymph node that was normal at baseline (<1.0 cm short axis) and increased to ≥1.0 cm short axis during follow-up.
 - b. At least a 20% increase in PBSD (sum of the longest diameter for all target visceral lesions plus the sum of the short axis of all the target lymph nodes at current evaluation) taking as reference the MSD (Section 11.41). In addition, the PBSD must also demonstrate an absolute increase of at least 0.5 cm from the MSD.
- Stable Disease (SD): Neither sufficient shrinkage to qualify for PR, nor sufficient increase to qualify for PD taking as reference the MSD.

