11.31 Measurement effect

- Complete Response (CR): No blood involvement.
- Partial Response (PR): 50% decrease in CD4 count or CD4:CD8 ratio ≤10 .
- Progressive Disease (PD): 50% increase from baseline ($\geq5,000$ CD4+cells in blood or CD4:CD8 ratio ≥15).
- Stable Disease (SD): Not CR, PR or PD.

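### For PR and CR90 responders without new tumours, skin regrowth to baseline is not a PFS event and does not end duration of response

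*Combined protocol and SAP*

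**What the plan says.** **Skin (11.211).** Every category is set against the baseline mSWAT.
- Partial response: "Cutaneous partial response rate (PR) = proportion of patients with a 50-90% baseline reduction of mSWAT score without the development of new tumors".
- Stable disease: "Stable cutaneous disease (SD) = <25% increase to <50% reduction in baseline mSWAT without the development of new tumors". A patient above that range also stays stable if the investigator attributes the rise to treatment inflammation or to unmasked subclinical disease.
- Progression: "Progressive cutaneous disease (PD) = greater than 25% increase in baseline mSWAT or the development of new tumors", subject to the same exception.
- Regrowth after response appears once: "Relapsed cutaneous disease = Any disease recurrence in those with complete response". There is no counterpart for CR90 or PR.

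**Nodes and viscera (11.226, 11.227).** The reference for progression is the lowest sum: "The minimum sum of the dimensions (MSD) is the minimum of the BSD and the PBSD". Growth of 20% over it is required. "In addition, the PBSD must also demonstrate an absolute increase of at least 0.5 cm from the MSD". A new malignant lesion also counts.

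**Blood (11.31).** The reference is baseline again: "Progressive Disease (PD): 50% increase from baseline", with limits on the CD4 count or CD4:CD8 ratio attached.

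**Analysis (16.11, 16.42).** All three response grades are treated alike: "Throughout Section 16.0, CR, CR90 or PR will be considered synonymous with" success. PFS ends at relapse or death, yet its censoring sentence speaks of progression. Duration of response covers CR, CR90 and PR, and ends at the first documented relapse.

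**The concern.** The protocol accepts that regrowth after a response matters, but gives it a skin event only in complete responders. Take two patients with a baseline mSWAT of 60. One clears to 0 and recurs to 1: that is relapse, and a PFS event. The other falls to 1 (CR90) and climbs to 60 without new tumours: that is stable disease, with no event. The better-controlled patient fails first.

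At stake are PFS and duration of response, both secondary goals in 2.23. Skin is the main source of timely information on loss of control, because mSWAT is scored at the end of every cycle (11.41). Imaging and T- and B-cell quantitation are scheduled only after cycle 4 and at end of treatment (4.1, 11.43).

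The gap is wider for duration of response. Since that endpoint ends only at relapse, a CR90 or PR patient has no defined skin end event at all, not even above 125% of baseline. PFS has a milder form of the same fault. Read literally, skin PD in a patient never in CR is not among its events, although the censoring sentence implies that it should be.

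**Working it through.** The plan gives no figure of its own here, so the check applies its definitions to example scores. Baseline mSWAT B = 60 is an assumption; the percentages do not depend on it. L is the lowest on-study score, with no new tumours.

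**Step 1. Current skin rule.** PD needs a score above 1.25 × B = 1.25 × 60 = 75. A score of 60 is a 0% change from baseline, so it is SD.

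| L | Best status | Status on return to 60 | PD threshold as multiple of L | Rise from L needed for PD |
|---|---|---|---|---|
| 30 | PR (50% reduction) | SD | 75/30 = 2.5 | more than 150% |
| 15 | PR (75% reduction) | SD | 75/15 = 5 | more than 400% |
| 6 | CR90 (90% reduction) | SD | 75/6 = 12.5 | more than 1150% |
| 0 | CR | already relapsed at any recurrence | not applicable | not applicable |

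**Step 2. Nodal and visceral rule on the same proportional falls.** Assume a baseline sum of 8 cm and a minimum M. PD starts at the larger of 1.2 × M and M + 0.5 cm.
- M = 4: max(4.8, 4.5) = 4.8 cm.
- M = 2: max(2.4, 2.5) = 2.5 cm.
- M = 0.8: max(0.96, 1.3) = 1.3 cm.

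Returns to 8 cm are rises of 100%, 300% and 900%, so each is PD well before baseline is regained.

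**Step 3. Consequence in 16.42.** A PR or CR90 patient back at baseline has not relapsed (11.211 reserves that for CR) and has not progressed (SD). Unless nodal, visceral or blood progression or death occurs, the patient is censored in PFS and the response has no skin end date.

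**Step 4. Size.** One event lowers the Kaplan-Meier estimate by S/n, where S is the estimate just before it and n the number at risk. With all 10 patients at risk this is 1/10 = 10 points. After, say, three censorings and no events it is 1/7 = 14.3 points. The error lasts until that patient has a later recorded event. The documents give no basis for predicting how many such patients there will be.

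**Step 5. Test of a possible event.** Let a PR or CR90 patient lose response when the score reaches L + 0.5 × B.
- L is above 0 (otherwise the patient is a CR), so the trigger lies above 0.5 × B. It cannot coincide with PR.
- L is at most 0.5 × B (otherwise there was no response), so the trigger is at most B. Full return to baseline is always caught.
- L = 6: 6 + 30 = 36, a 40% reduction. L = 30: 30 + 30 = 60, exactly baseline. The wording must therefore be at least 50%; a more-than-50% rule would miss the second patient on return to 60.

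**The case against.** **Different references are not in themselves a contradiction.** A sum of diameters and mSWAT are different instruments, and blood PD also uses baseline, so skin is not the only compartment without a lowest-value reference. With two scheduled post-baseline scans, the nodal minimum has little room to operate. This stands. The point rests instead on the unequal treatment of CR and of CR90 or PR within 11.211, and on the event wording in 16.42.

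**A reader might infer that every responder is affected, or that PFS cannot register loss of control until skin is worse than at entry.** The documents do not support that. Any recurrence after CR is relapse, new tumours are PD whatever the mSWAT, and nodal, visceral or blood progression can come first.

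**A reader might infer that the headline response rate is inflated.** It is not. The primary analysis uses mSWAT at baseline and cycle 9 and makes no use of the PD definition. A patient back at baseline at cycle 9 is not a success.

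**Section 16.42 may use relapse more broadly than 11.211**, since it applies the word to CR90 and PR in duration of response. That is possible, but the broader meaning is then undefined, and the same edit is needed.

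**The practical weight is limited.** PFS is secondary, described by Kaplan-Meier without a test, and accrual stops at 10. The error may be a delay rather than a permanently missed event. This stands, and keeps the point below the level of a threat to the trial's main result.

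**Changing 11.211 would alter treatment.** Under 13.1 and 13.2, SD continues therapy and PD ends it. This stands, so the repair should not be made there.

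**Conclusion.** The point holds for PR and CR90 responders without new tumours. Their skin disease can return fully to baseline, and up to 25% beyond it, without an event in PFS, and duration of response has no defined skin end for them. Both endpoints are overstated when such patients occur.

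The size is conditional: about 10 Kaplan-Meier points per patient if all 10 are at risk, a different step once others have been censored, and nothing if no such patient arises. The conclusion assumes that relapse in 16.42 carries its only definition, the one in 11.211. The primary endpoint is not affected. The documents do not show that the skin criteria are wrong for deciding treatment, and this point makes no such claim.

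**What to change.** Amend 16.42, for analysis only:
1. State that the PFS event is the first of progression (skin, nodal, visceral or blood), relapse after CR, or death, and use the same terms in the censoring sentence.
2. For both PFS and duration of response, add a loss-of-response event for PR and CR90 patients, for example a rise from the lowest mSWAT of at least 50% of the baseline score. The 50% is an assumption not given in the documents. The sponsor should check it against the consensus criteria that 1.23 says the endpoints follow.
3. Carry over the inflammation and unmasking exception from 11.211.
4. Require confirmation only where a further mSWAT is scheduled. Scores are planned each cycle and at the 30- and 90-day clinical follow-up visits, but the survival follow-up table in 4.2 lists none.
5. Report PFS under the current rule as a sensitivity analysis.

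Leave 11.211 unchanged as it governs treatment. Whether 11.211, 11.227, 13.1 and 13.2 should be reconciled for treatment decisions is for the clinical team.

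The cost is a few lines of text and no new data collection. PFS and duration of response will come out somewhat shorter, and the analysis will carry a skin event that differs from the treatment definition, which the report must say.
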